3.2 DRUG ADMINISTRATION

3.2.1 EP0057

EP0057 will be diluted with 5% dextrose for injection (D5W) to a total volume of 500 mL and should be infused intravenously as described in section 14.1.6 over 60-75 minutes. Nothing else should be added to the bag.

The EP0057 infusion should begin immediately after preparation and diluted EP0057 infusion solution not used within 6 hours should be destroyed following institutional practices.

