1.2.8 EP0057 phase I clinical trial

Patients with advanced solid malignancies were enrolled to an open-label, single-arm, dose-escalation study, in which EP0057 was administered intravenously over 60 min among two dosing schedules, initially weekly at 6, 12, and 18 mg/m² and later bi-weekly at 12, 15, and 18 mg/m². The MTD was determined at 15 mg/m² bi-weekly, and an expansion phase 2a study was completed. Sixty-two patients (31 male; median age 63 years, range 39-79) received treatment. Bi-weekly dosing was generally well tolerated with myelosuppression being the dose-limiting toxicity. Among all phase 1/2a patients receiving the MTD ($n=44$), most common grade 3/4 adverse events were neutropenia (Grade 3 neutropenia = 9% and no grade 4) and fatigue (Grade 3 fatigue = 9%, no grade 4). Evidence of systemic plasma exposure to both the polymer-conjugated and unconjugated CPT was observed in all treated patients. Mean elimination unconjugated CPT Tmax values ranged from 17.7 to 24.5 h, and maximum plasma concentrations and areas under the curve were generally proportional to dose for both polymer-conjugated and unconjugated CPT. Best overall response was stable disease in 28 patients (64 %) treated at the MTD and 16 (73 %) of a subset of NSCLC patients. Median progression-free survival (PFS) for patients treated at the MTD was 3.7 months and for the subset of NSCLC patients was 4.4 months.

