1.2.11 EP0057 (CRLX101) Clinical Development Overview

As of 12 March 2016, there have been 5 clinical trials sponsored by Cerulean: CRLX-001, CRLX-002, CRLX101-208, CRLX101-209, and CRLX101-102.

- Studies CRLX-001 and CRLX-002 have been completed; studies CRLX101-208, CRLX101-209, and CRLX101-102 are ongoing.
- 246 subjects received CRLX101/EP0057 at doses ranging from 6 to 18 mg/m² in the 5 cerulean-sponsored trials.

There have been 7 Investigator-sponsored trials (ISTS) with EP0057 (named CRLX101 at the time), (see **Table 4** for details); as of 12 March 2016, 138 subjects received at least 1 dose of EP0057 in the ISTs at doses ranging from 12 to 15 mg/m².

- A total of 384 subjects across all studies have received at least 1 dose of CRLX101. When tested in the QOW schedule, the MTD/RP2D of EP0057 monotherapy was determined to be 15 mg/m².
- EP0057 has been generally well-tolerated, and has shown preliminary antitumor activity in subjects with solid tumors such as with gastroesophageal, lung, and ovarian cancers.

As of 12 March 2020, there have been 6 clinical trials sponsored by Cerulean Pharma (prior to 17 April 2017) and BlueLink Genetics (as of 17 April 2017). Overall, 286 subjects received at least 1 dose of EP0057 at doses ranging from 6 to 18 mg/m² in these 6 BlueLink Genetics-sponsored studies. There have been 8 Investigator-sponsored trials with EP0057 in which 193 subjects received at least 1 dose of EP0057 at starting doses ranging from 12 to 15 mg/m². When tested in the every-other-week schedule, the MTD/recommended phase 2 dose (RP2D) of EP0057 monotherapy was determined to be 15 mg/m². EP0057 has been generally well-tolerated, and has shown preliminary antitumor activity in subjects with solid tumors.

Overall Safety Assessment from these trials indicated:

- Infusion-related reactions, cystitis, hematologic toxicity, and gastrointestinal disorders have been recognized as the risks associated with EP0057.
- Infusion-related hypersensitivity reactions have been well managed with the mandatory premedication and slower rate of infusion.
- Cystitis symptoms have been well managed with IV hydration before and after the EP0057 infusion. In addition, the impact of urine alkalization (oral and/or IV) on the incidence and severity of cystitis in subjects treated with EP0057 continue to be evaluated.

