3.2.1.1 Premedication Prior to EP0057 Treatment and Pre and Post Hydration

Subjects will receive up to 1,000 ml of 0.9% normal saline solution IV hydration before and after administration of EP0057 to reduce risk of cystitis adverse reaction. Hydration levels should be adjusted as needed by the Investigator based on any underlying health conditions of the subject.

Hypersensitivity reaction (HSR) have been observed in a small number of subjects treated with EP0057. Most HSR associated with EP0057 are mild and moderate, reversible upon study drug interruption. In general, subjects restarted EP0057 infusion at a slower infusion rate without recurrence. In addition to the mandatory premedication to prevent HSR, the duration of EP0057 infusion must be prolonged from 1 hour to approximately 2 hours.

Appropriate resuscitation equipment should be available in the room and a physician readily available during the period of study drug infusion.

Subjects should be pre-medicated with the following 3 drug classes 30-120 minutes* prior to start of EP0057 infusion to reduce likelihood of hypersensitivity adverse reactions:

- a corticosteroid (dexamethasone 20 mg IV) 30-120 minutes prior to start of EP0057
- an antihistamine (diphenhydramine 50 mg PO)
- an H2 antagonist (ranitidine 50 mg IV)

Premedication with antiemetics such as a 5-HT3 receptor antagonist are to be administered to reduce the potential for nausea. Suggested antiemetics include dolasetron (PO), granisetron (PO or IV) or ondansetron (PO or IV) 30-120 minutes prior to starting EP0057 infusion.

The example medications, route of administration, and dose indicated should be the medication-of-choice if clinically feasible. It is acknowledged that the premedication regimen may be altered for patient safety during the study (for example, if a patient experiences a hypersensitivity/infusion reaction related to study drug, the premedication regimen may be altered for subsequent cycle dosing based on the investigator's discretion).

* Contact study team if the time after pre-medications exceeds 120 minutes.

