3.3.4 Management of the hypersensitivity/infusion reactions

Table 10. Management of the hypersensitivity/infusion reactions

Hypersensitivity reaction	
Grade 1 or 2	
Stop infusion immediately, continue hydration fluids and provide medications as indicated per institutional guidelines.
 
If symptoms resolve within 1-2 hours, at Investigator's discretion may re-start study drug administration at slower rate (i.e. 2x slower rate) and increase rate slowly to complete administration of full dose.
 
OR
 
Hold dose administration on day of event, and resume treatment at next scheduled day at same dose level.
 
At Investigator's discretion may administer subsequent dose using a desensitization protocol as per institutional guidelines.

Grade 3 or 4	
Stop infusion immediately and administer medical support as indicated per institutional guidelines.
 
Hold dose administration on day of event.
 
Review with study Principal Investigator to determine whether to discontinue from study drug treatment. Confirm that rate of administration was appropriate and premeds were given as suggested.

Administration of EP0057 should be over 2 hours (using the following infusion schedule) with additional pre-medications (dexamethasone 20mg IV, ranitidine 50mg IV, acetaminophen 650mg PO, ondansetron 16mg PO or IV and Benadryl 50mg PO).

EP0057 in 500ml 5% dextrose IV infusion

15mL/hr for 15 minutes, then increase to
30mL/hr for 15 minutes, then increase to
60mL/hr for 15 minutes, then increase to
120mL/hr for 15 minutes, then increase to

240mL/hr for 15 minutes, then increase to
480mL/hr for 15 minutes, then increase to
528mL/hr for 30 minutes to complete infusion

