8.5 SAFETY REPORTING CRITERIA TO THE PHARMACEUTICAL COLLABORATORS

8.5.1 Ellipses Reporting Requirements

The study team will report every SAE, regardless of suspected causality, occurring after the patient begins taking study drug and until 30 days after the patient has stopped study treatment to Ellipses within 24 hours of learning of its occurrence. The MedWatch 3500A or equivalent form will be used to report all SAEs. The study team will report any SAE experienced after this 30 day period only if there is a causal relationship to the study drug.

Recurrent episodes, complications, or progression of the initial SAE will be reported by the study team as follow-up to the original episode within 24 hours of follow-up information receipt. An SAE occurring at a different time interval or otherwise considered completely unrelated to a previously reported one will be reported separately as a new event. The investigator will assess and record the relationship of each SAE to each specific study drug (if there is more than one study drug).

SAEs will be reported to:

- Ellipses pharmacovigilance vendor, Simbec-Orion:
[contact] (Or alternatively by fax to [contact] or Back-up [contact])
- Ellipses contacts: [name] at [contact] Other Adverse Events of Special Interest

For all subjects, the following adverse events are categorized as Adverse Events of Special Interest (AESI) for EP0057:

- infusion-related hypersensitivity reaction(s) of any Grade
- any newly developed cystitis (including grade 1) in subjects without cystitis at baseline

The study team will report any occurrence of cystitis or patient hypersensitivity/allergic reactions a patient experiences associated with EP0057 to Ellipses (via Simbec-Orion) within 24 hours of learning of its occurrence using MedWatch 3500A or equivalent form.

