14.1.6 Dosage and Administration

See Sections 3.2 and 3.3 for the dose levels and administration of EP0057 to be evaluated in this study.

See Section 3.3.4 for management of any EP0057 infusion related/hypersensitivity reactions.

The second and subsequent dose of EP0057 may be delayed if related AEs have not resolved to grade 1 or better. If a dose of EP0057 is delayed, then the subsequent dose should be administered 2 weeks later to avoid significant carry-over of unconjugated plasma CPT from one dose to the next (see Section 3.3). However, the maximum delay for AEs to resolve is 21 days beyond which the patient will be taken off treatment.

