14.1.7 Premedication and Hydration

The premedication prior to EP0057 treatment and pre and post hydration and additional prevention measurements to prevent hypersensitivity/infusion reaction have been described in Section 3.2.1.1.

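### Section 3.2.1 still gives a 60-75 minute EP0057 infusion, although its own subsection 3.2.1.1 requires about 2 hours to prevent hypersensitivity reactions

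*Combined protocol and SAP*

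**What the plan says.** Section 3.2.1 is the EP0057 dosing instruction. It has the drug diluted in 5% dextrose to 500 mL and says it "should be infused intravenously as described in section 14.1.6 over 60-75 minutes".

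Section 3.2.1.1, a subsection of 3.2.1, covers premedication and hydration. Having described hypersensitivity reactions, it says that, on top of the mandatory premedication, "the duration of EP0057 infusion must be prolonged from 1 hour to approximately 2 hours".

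Four other places bear on the point:

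- Section 14.1.6, the target of the pointer in 3.2.1, gives no duration or rate. It says "See Sections 3.2 and 3.3 for the dose levels and administration of EP0057 to be evaluated in this study" and names 3.3.4 for the management of reactions.
- Section 14.1.7 treats 3.2.1.1 as the source for prevention, stating that "additional prevention measurements to prevent hypersensitivity/infusion reaction have been described in Section 3.2.1.1".
- Section 3.3.4, on managing reactions, sets out a stepped 2-hour infusion schedule.
- Section 1.2.8 describes the earlier single-agent trial, in which "EP0057 was administered intravenously over 60 min among two dosing schedules".

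**The concern.** Sections 3.2.1 and 3.2.1.1 are both current text and give different durations for the same infusion. Staff who act on the 3.2.1 sentence alone would infuse faster than the preventive rule allows, and following the cross-reference to 14.1.6 brings them back to where they started.

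The duration matters for safety. Section 1.2.11 says "Infusion-related hypersensitivity reactions have been well managed with the mandatory premedication and slower rate of infusion", so the slower rate is one of the two measures credited with control. Section 8.5.1 lists "infusion-related hypersensitivity reaction(s) of any Grade" as an adverse event of special interest, to be reported within 24 hours. After a Grade 3 or 4 reaction, section 3.3.4 tells staff: "Confirm that rate of administration was appropriate and premeds were given as suggested". That check forms part of the review that decides whether the patient stops the drug. A 70-minute infusion passes it under 3.2.1 and fails it under 3.2.1.1.

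**Working it through.** **Inputs.** Volume 500 mL and duration 60-75 minutes (3.2.1); duration about 2 hours (3.2.1.1); Phase II dose 12 mg/m² (3.1); stepped schedule (3.3.4); reconstitution up to 30 minutes (14.1.4); use within 6 hours of reconstitution (14.1.5).

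**1. The protocol's own 2-hour schedule (3.3.4).** Volume is the sum of rate × time over six 15-minute steps and one 30-minute step:

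(15 + 30 + 60 + 120 + 240 + 480) × 0.25 h + 528 × 0.5 h = 236.25 + 264 = 500.25 mL in 120 minutes.

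The schedule therefore delivers the full bag in 2 hours. Volume delivered by the times given in 3.2.1:

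- by 60 minutes: (15 + 30 + 60 + 120) × 0.25 = 56.25 mL, or 11% of 500 mL
- by 75 minutes: 56.25 + 240 × 0.25 = 116.25 mL, or 23%

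It cannot be reconciled with a 60-75 minute infusion.

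**2. Mean rates under the two instructions.** Mean rate = volume / duration; dose rate = 12 mg/m² / duration.

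| Duration | Mean rate (mL/h) | Dose rate (mg/m² per hour) | Ratio to 2 h |
|---|---|---|---|
| 60 min (3.2.1) | 500 / 1.00 = 500 | 12 / 1.00 = 12 | 500 / 250 = 2.0 |
| 75 min (3.2.1) | 500 / 1.25 = 400 | 12 / 1.25 = 9.6 | 400 / 250 = 1.6 |
| 120 min (3.2.1.1) | 500 / 2 = 250 | 12 / 2 = 6 | 1.0 |

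**3. Which text governs.** Section 3.2.1.1 is mandatory in its wording, names the 1-hour duration and replaces it; 3.2.1 says only what should be done. Section 14.1.7 sends the reader to 3.2.1.1 for prevention. The shorter duration matches the 60-minute infusion of the earlier trial (1.2.8), which is consistent with text that was carried over and not revised. That last step is an inference.

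**4. Whether 2 hours fits the use limit.** For an uninterrupted infusion, 0.5 h reconstitution + 2 h infusion = 2.5 h, within the 6 h allowed.

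**The case against.** The strongest objection is that 60-75 minutes is the default and 2 hours applies only after a reaction. The stepped schedule sits under reaction management in 3.3.4 and comes with additional premedication, including acetaminophen, which 3.2.1.1 does not list. Table 10 allows a restart at half the rate, and twice 1 hour is 2 hours. In 3.2.1.1 the sentence just before the 2-hour rule concerns patients who restarted more slowly after a reaction. This reading can be argued for 3.3.4, but the words of 3.2.1.1 do not support it: the 2-hour sentence carries no condition and is tied to premedication given before the infusion. Where 3.2.1.1 does mean a change after a reaction, as with altering the premedication, it says so. If the sponsor intends the narrower rule, the text still needs correcting.

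The other objections stand in part:

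- **The rates are averages.** The 3.3.4 schedule ends at 528 mL/h, above the 400-500 mL/h mean, and gives 264 of about 500 mL in its last 30 minutes. Where that schedule is used, the protection lies in the slow start. The factor of 1.6-2.0 describes mean rate only.
- **Use limit after an interruption.** Suppose a reaction at 15 minutes, 2 h to resolve, and the remaining 1.75 h of infusion run at half rate throughout (3.5 h). The total with reconstitution is 0.5 + 0.25 + 2 + 3.5 = 6.25 h, just over 6 h. Table 10 lets the rate be raised again, so the actual time may be shorter. The 2.5 h figure covers an uninterrupted infusion only.
- **PK Table 12** also puts the end of infusion at 1 hour, but it applies to Phase I, which is complete.
- **Practical weight.** The stricter rule comes in the very next subsection, and premedication, resuscitation equipment and a readily available physician apply under either duration.

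**Conclusion.** The concern holds. Section 3.2.1 contradicts the unconditional rule in 3.2.1.1, and its cross-reference does not resolve the conflict. Following 3.2.1 as written gives a mean infusion rate 1.6 to 2.0 times that of a 2-hour infusion. Confidence in the contradiction is high. That the 60-75 minute phrase was overlooked in an update is a likely explanation and cannot be proved from the documents.

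The documents give no reaction rate by infusion duration, so the harm cannot be sized. No efficacy result, sample size or error rate depends on this. It should be corrected because it is a dosing instruction on a named safety risk.

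**What to change.** In section 3.2.1, change the duration to approximately 2 hours and replace the pointer to 14.1.6 with one to 3.2.1.1. This removes the contradiction. It costs a few words, with no change needed elsewhere in the protocol, in data collection or in the analysis.

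A useful extra would be a sentence saying whether the stepped schedule in 3.3.4 applies to every infusion or only after a reaction, since 3.2.1.1 gives a duration but no rates.

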3.2.1.1 Premedication Prior to EP0057 Treatment and Pre and Post Hydration

Subjects will receive up to 1,000 ml of 0.9% normal saline solution IV hydration before and after administration of EP0057 to reduce risk of cystitis adverse reaction. Hydration levels should be adjusted as needed by the Investigator based on any underlying health conditions of the subject.

Hypersensitivity reaction (HSR) have been observed in a small number of subjects treated with EP0057. Most HSR associated with EP0057 are mild and moderate, reversible upon study drug interruption. In general, subjects restarted EP0057 infusion at a slower infusion rate without recurrence. In addition to the mandatory premedication to prevent HSR, the duration of EP0057 infusion must be prolonged from 1 hour to approximately 2 hours.

Appropriate resuscitation equipment should be available in the room and a physician readily available during the period of study drug infusion.

Subjects should be pre-medicated with the following 3 drug classes 30-120 minutes* prior to start of EP0057 infusion to reduce likelihood of hypersensitivity adverse reactions:

- a corticosteroid (dexamethasone 20 mg IV) 30-120 minutes prior to start of EP0057
- an antihistamine (diphenhydramine 50 mg PO)
- an H2 antagonist (ranitidine 50 mg IV)

Premedication with antiemetics such as a 5-HT3 receptor antagonist are to be administered to reduce the potential for nausea. Suggested antiemetics include dolasetron (PO), granisetron (PO or IV) or ondansetron (PO or IV) 30-120 minutes prior to starting EP0057 infusion.

The example medications, route of administration, and dose indicated should be the medication-of-choice if clinically feasible. It is acknowledged that the premedication regimen may be altered for patient safety during the study (for example, if a patient experiences a hypersensitivity/infusion reaction related to study drug, the premedication regimen may be altered for subsequent cycle dosing based on the investigator's discretion).

* Contact study team if the time after pre-medications exceeds 120 minutes.

3.2.2 Olaparib

Olaparib tablet at the appropriate dose level will be given orally on days 3-13* and days 17-26* twice daily (*there should be at least a 48-hour window between olaparib and EP0057 except dose level 5B which allows the window to be abbreviated to 24 hours). The correct number of 25 mg, 100 mg, 150 mg or 200 mg tablets comprising the appropriate dose should be taken at the same times each day with approximately 240 mL of water. A light snack (biscuits/ toast) is advised at the time of dosing to help alleviate nausea but no specific timing needs to be observed. The olaparib tablets should be swallowed whole and not chewed, crushed, dissolved or divided.

Olaparib will be dispensed at the start of each cycle. Patients will be provided with a pill diary ([Appendix C](#), Section 16.3), instructed in its use, and asked to bring it with them to each appointment.

For Phase II, it is recommended, but not required, that growth factors be given prophylactically starting cycle 1 on the phase II part of the study. Please note that G-CSF should not be used within at least 24 hours of the last dose of EP0057 administration.

If vomiting occurs shortly after the olaparib capsules are swallowed, the dose should only be replaced if all of the intact capsules can be seen and counted. Should any patient enrolled on the study miss a scheduled dose, the patient will be allowed to take the scheduled dose up to a maximum of 2 hours after that scheduled dose time. If greater than 2 hours after the scheduled dose time, the missed dose should not be taken, and the patient should take their allotted dose at the next scheduled time.

Olaparib can be taken continuously in cases where EP0057 is missed for any reason.

3.3 DOSE MODIFICATIONS

The dose levels and the general approach to dose modification of EP0057 and olaparib are shown below. AEs should be treated with the appropriate maximum intervention, and dose reductions should be clearly documented in the note.

3.3.1 General Recommendation for Dose Modification

Table 6. Olaparib Dosage Schedule

Dose Level	Olaparib dosage schedule		
	Starting dose	First dose reduction	Second dose reduction

-1	100 mg twice daily	75 mg twice daily	50 mg twice daily
1	100 mg twice daily	75 mg twice daily	50 mg twice daily
2	150 mg twice daily	100 mg twice daily	75 mg twice daily
3	200 mg twice daily	150 mg twice daily	100 mg twice daily
4 and 5	300 mg twice daily	250 mg twice daily	200 mg twice daily
4R (RP2D)	250 mg twice daily	200 mg twice daily	150 mg twice daily

Table 7. EP0057 Dosage Schedule

Dose Level	EP0057 dosage schedule		
	Starting dose	First dose reduction	Second dose reduction
-1	9 mg/m2 q 2weeks	6 mg/m2 q 2weeks	4 mg/m2 q 2weeks
1-4 & 4R	12 mg/m2 q 2weeks	9 mg/m2 q 2weeks	6 mg/m2 q 2weeks
5	15 mg/m2 q 2weeks	11 mg/m2 q 2weeks	7 mg/m2 q 2weeks

3.3.2 Dosing Delays/Dose Modifications and Management of Toxicities

- In the case of toxicity, appropriate medical treatment should be used (including anti-emetics, anti-diarrheals, etc.).
- Once a patient has a dose reduction for toxicity, the dose will not be increased.
- A maximum of 2 dose reductions is permitted
- If either agent is discontinued due to toxicity, the patient may continue on the other agent.
- Participants continuing to experience toxicity at the off treatment visit will be contacted for additional assessments until the toxicity has resolved or is deemed irreversible. Patients must remain on the study to have additional assessment.
- For AEs that are unrelated to the study drugs, study drug may be held for up to 21 days at the discretion of the PI.
- The associate investigator and/or PI will determine whether one or both drugs are responsible for an observed toxicity and will manage that toxicity as described below.

